2.7 Table of endpoints/outcomes

Objectives	Outcome Measures	Timepoint of evaluation of this outcome measure
Primary Objective To assess the efficacy of tDCS treatment.	Clinical response as measured by MADRS score improvement of >= 50% following the course of tDCS treatment	End of tDCS sessions (visit 21)
Secondary Objectives To assess the acceptability and safety of the intervention	Participant retention at the end of the treatment who have completed a minimum of 15 tDCS sessions Participant acceptability questionnaire scales tDCS Adverse Events Questionnaire	End of tDCS sessions (visit 21) At each session

3 TRIAL DESIGN

The present study is a proof-of-concept trial to assess the efficacy, acceptability and safety of tDCS treatment for bipolar depression within a community-based setting.

4 TRIAL SETTING

School of Psychology, University of East London

5 PARTICIPANT ELIGIBILITY CRITERIA

5.1 Bipolar depression sample

5.1.1 Inclusion criteria

- participants capable of giving informed consent
- male and female
- minimum of 18 years of age
- diagnosis of bipolar disorder based on DSM-5 criteria, with a current depressive episode of at least a moderate severity
- diagnosis will be confirmed by the Mini-International Neuropsychiatric Interview
- Depressive symptoms severity will be assessed using the Montgomery–Åsberg Depression Rating Scale (MADRS) with a minimum score of 18, indicating at least a moderate severity of symptoms.
- Being on a stable dosage of mood stabilising medication for a minimum of two weeks or not taking any medications for a minimum of two weeks. We would like to emphasize that we would not ask participants to stop their medications in order to take part in the study

5.1.2 Exclusion criteria

- any concurrent psychiatric disorder, including obsessive compulsive disorder
- having a significant risk of suicide
- score greater than 8 in the Young Mania Rating Scale
- exclusion criteria for tDCS, including having a scalp or skin condition (e.g. psoriasis or eczema); if contact with the scalp is not possible; having metallic implants, including intracranial electrodes, surgical clips, shrapnel or a pacemaker

- history of epilepsy
- history of a seizure which resulted in a loss of consciousness
- neurological disorder or history of migraines

5.2 Healthy control sample

5.2.1 Inclusion criteria

- participants capable of giving informed consent
- male and female
- minimum of 18 years of age

5.2.2 Exclusion criteria

- any concurrent psychiatric disorder, including obsessive compulsive disorder
- having a significant risk of suicide
- score greater than 8 in the Young Mania Rating Scale

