2.6 Exploratory endpoints/outcomes

Exploratory measures:

- i. Trained rater measure of depressive symptoms: Montgomery–Åsberg Depression Rating Scale (MADRS) remission rate
- ii. Self-report measure of depressive symptoms: Patient Health Questionnaire (PHQ-9)
- iii. Trained rater measure of anxiety symptoms: Hamilton Anxiety Scale (HAMA)
- iv. Trained rater measure of manic symptoms: Young Mania Rating Scale (YMRS)
- v. Self-report measure of disability and impairment: Sheehan Disability Scale (SDS)
- vi. Self-report Quality of Life Enjoyment and Satisfaction Questionnaire (Q-LES-Q)
- vii. Self-report acceptability of tDCS from healthy controls.
- viii. EEG recordings will be acquired during an eyes-closed resting state for 10 minutes and eyes open resting state for 10 minutes using a mobile EEG device in participants' homes (Muse EEG; <https://choosemuse.com/>) (Hashemi et al., 2016). Resting state EEG will be acquired at baseline for healthy controls and at 2 timepoints for participants with bipolar depression: 1) at baseline, and 2) at the end of the 6-week course of treatment. EEG coherence, a measure of neural connectivity, will be examined as a potential surrogate outcome measure (Minuissi et al., 2012).
- ix. Neuropsychological measures: verbal learning (Rey Auditory Verbal Learning Test (RAVLT)) and information processing speed (Symbol-Digit Modalities Test (SDMT)) will be assessed in participants' homes. Neuropsychological assessments will be delivered to participants and administered by a research team member via video call. Our pilot data indicates feasibility and acceptance of the neuropsychological assessments as all participants had completed the assessments (26 out of 26 participants). The measures will be acquired at baseline for healthy controls, and at 2 timepoints for participants with bipolar depression: 1) at baseline, and 2) at the end of the 6-week course of treatment.

Exploratory outcomes:

- 1) MADRS score ≤ 9 following the course of tDCS
- 2) Improvement in self-reported depressive symptoms as measured by PHQ-9
- 3) Improvement in anxiety symptoms as measured by HAMA
- 4) No significant increase in manic symptoms as measured by YMRS score >13
- 5) Improvement in disability experience as measured by SDS
- 6) Improvement in quality of life as measured by Q-LES-Q
- 7) Healthy control participant baseline acceptability questionnaire.

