6.1 Recruitment

Based on an effect size of $d = 0.70$ (Meron et al., 2015; Mutz et al., 2018) following a 6-week course of tDCS treatment (consisting of 15-21 sessions) with 90% power, we will enrol 50 participants to achieve a sample size of 45 participants with bipolar depression who will complete the course of treatment, based on a 10% attrition rate.

We will enrol 35 healthy controls to complete baseline activities.

Our participants have a wide ethnic diversity. In our pilot study, 38% of participants were of non-White ethnicity i.e. 12% Black/African Caribbean, 4% Pakistani, 4% Chinese, 16% Mixed ethnic background, and 62% English or any White background. Recruitment will be from primary care, consulting psychiatrists, print and social media advertisements.

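### Healthy controls who give baseline EEG and cognitive data are not held to the neurological exclusions applied to patients

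*Combined protocol and SAP*

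**What the plan says.** Section 6.1 sets the size of the control group: "We will enrol 35 healthy controls to complete baseline activities". Section 5.2 holds its entry rules. Under 5.2.1 a control must be able to consent, may be of either sex, and must have a "minimum of 18 years of age". Section 5.2.2 then lists three exclusions: "any concurrent psychiatric disorder, including obsessive compulsive disorder", "having a significant risk of suicide" and "score greater than 8 in the Young Mania Rating Scale". The word healthy is not defined further.

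For patients, Section 5.1.2 opens with the same three exclusions. It then lists tDCS contraindications (scalp and skin conditions, metallic implants), followed by "history of epilepsy", a past seizure with loss of consciousness, and "neurological disorder or history of migraines".

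Section 2.6 collects resting EEG from controls once, at baseline. For verbal learning (RAVLT) and processing speed (SDMT) it says: "The measures will be acquired at baseline for healthy controls". Patients have both sets of measures at baseline and again at the end of treatment.

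**The concern.** A healthy control group measured on brain activity and cognition should at least be free of the neurological conditions for which patients are turned away. Here the screening runs the other way: patients are cleared of epilepsy, seizures, neurological disorder and migraine, and controls are not.

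Epilepsy and neurological disease can plausibly alter resting EEG, verbal learning and processing speed. If some controls have such a condition, a baseline difference between the groups reflects bipolar depression and unequal screening together. It could hide a real difference or distort its size. Section 1 says the findings will feed the design of a sham-controlled trial, so a control group that is hard to interpret would weaken what is carried forward on these measures.

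**Working it through.** The plan gives no figure to reproduce on this point, so the check is a comparison of the texts.

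**Step 1. The two exclusion lists side by side.**

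| Ground for exclusion | Patients (5.1.2) | Controls (5.2.2) |
|---|---|---|
| Concurrent psychiatric disorder | yes | yes, identical wording |
| Significant suicide risk | yes | yes |
| YMRS above 8 | yes | yes |
| Scalp, skin or implant contraindications to tDCS | yes | no |
| Epilepsy | yes | no |
| Seizure with loss of consciousness | yes | no |
| Neurological disorder | yes | no |
| Migraine history | yes | no |

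The control list repeats the first three patient items and stops. The scalp and implant items concern wearing the device, and no tDCS course is described for controls, so their absence is understandable. The last four rows are the gap.

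**Step 2. Does another section close it?** The inclusion criteria in 5.2.1 do not. Section 6.1.2 describes the screening assessment for patients only. Section 11 lists pre-existing conditions at screening, but it has no column for controls, and recording a condition does not exclude anyone. Its eligibility row can only refer back to Section 5. No criterion elsewhere removes a control with epilepsy or neurological disease.

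**Step 3. Which outcomes are touched?** The primary outcome (9.3.2) is a response proportion among enrolled trial participants. The secondary outcomes (9.3.3) are retention, acceptability and adverse events with the intervention. None uses control EEG or cognitive data. Those data appear only among the exploratory measures in 2.6.

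**Step 4. Can the bias be sized?** If a share p of controls has one of these conditions, and it shifts their mean on a measure by an amount s, the control mean moves by p × s. The documents give neither p nor s for any measure. The conditions also need not act in the same direction, so shifts could partly cancel. Nor is there a planned precision to set the bias against: the effect size and power in 6.1 and 9.1 concern patients, and the figure of 35 controls has no derivation.

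**The case against.** **No patient-control comparison is planned.** This is correct. The EEG hypothesis and the machine-learning prediction in 2.6 concern improvement and response to treatment, which controls measured once cannot supply. The only listed outcome specific to controls is their acceptability questionnaire, and Section 9 never mentions them. The bias therefore attaches to an analysis that a reader must infer. The inference is a fair one, because a single baseline EEG and cognitive assessment in controls has no other evident use, but it remains an inference.

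**The neurological items may be stimulation precautions.** In 5.1.2 they directly follow the tDCS contraindications, and no tDCS course is described for controls. The documents do not state this reason. If it is the reason, it explains why the items were written for patients. It does not justify leaving them out for a group assessed on EEG and cognition.

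**Staff would read the word healthy strictly.** Perhaps so, but no written rule requires it, and different staff may draw the line in different places.

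**A reader might go further and say that controls should also be free of past mood disorder, or need a MADRS ceiling.** The documents do not support this as an error. The word concurrent is the same in both lists, so it is not a looser rule for controls, and it already covers a current depressive disorder. Whether to admit people with remitted illness or sub-threshold symptoms is a choice between broad and highly selected controls, and the plan may make it either way.

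**Conclusion.** The gap is real and minor. As written, 5.2.2 admits a control with epilepsy, a past seizure with loss of consciousness, neurological disorder or migraine, and each of these excludes a patient. A baseline comparison of EEG, RAVLT or SDMT between the groups would carry that difference in screening.

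The conclusion rests on two assumptions: that the control data will be compared with the patients' baseline data, and that at least some of these conditions affect the measures. The size of the effect is unknown. A reader might put a figure on it by assuming a prevalence and a shift, but any such figure would come wholly from the assumptions. It would also be wrong to infer that the trial's efficacy, acceptability or safety results are compromised, since none of them draws on the control EEG or cognitive data.

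**What to change.** Add to 5.2.2 the four neurological items already in 5.1.2: epilepsy, seizure with loss of consciousness, neurological disorder and history of migraine. State that they are checked by screening questions put to each control, because 6.1.2 describes screening for patients only.

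If controls are already enrolled, ask them the same questions. Any with such a history should be excluded from the EEG and cognitive comparison, or the comparison should be reported with and without them. The choice should be written down before the data are compared. If the sponsor prefers to keep the broader control group, the protocol should give the reason.

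The cost is a short eligibility amendment, a few added screening questions and a few volunteers turned away. Nothing changes for patients.

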6 TRIAL PROCEDURES

The Schedule of Events is presented in table format in Appendix 2.

6.1 Recruitment

Based on an effect size of $d = 0.70$ (Meron et al., 2015; Mutz et al., 2018) following a 6-week course of tDCS treatment (consisting of 15-21 sessions) with 90% power, we will enrol 50 participants to achieve a sample size of 45 participants with bipolar depression who will complete the course of treatment, based on a 10% attrition rate.

We will enrol 35 healthy controls to complete baseline activities.

Our participants have a wide ethnic diversity. In our pilot study, 38% of participants were of non-White ethnicity i.e. 12% Black/African Caribbean, 4% Pakistani, 4% Chinese, 16% Mixed ethnic background, and 62% English or any White background. Recruitment will be from primary care, consulting psychiatrists, print and social media advertisements.

6.1.1 Participant identification

Potential participants will be referred by their GPs and psychiatrists as well as recruited by publicity, leaflets and websites.

Only a member of the patient's existing clinical care team will have access to patient records without explicit consent in order to identify potential participants, to check whether they meet the inclusion criteria and to make the initial approach to patients.

Participants will be identified by their responsible physician or will be identified by self-referral. All participants will be required to be under the care of a GP for study participation.

6.1.2 Screening

The screen assessment for participants with bipolar depression requires a DSM-5 diagnosis of major depressive disorder by a MINI interview assessment and a minimum score of 18 on the MADRS. The maximum duration between screening and recruitment is 20 days.

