Trial Name:

Community-based transcranial direct current stimulation treatment for bipolar depression

Document date:

17/07/2023

Principal Investigator	[name][name], University of East London, [name]
Protocol contributors	[name], Centre for Affective Disorders, Institute of Psychiatry, Psychology and Neuroscience, King's College London [name], Technische Universität Dresden, Germany [name], Technische Universität Dresden, Germany [name], University College London
Clinicaltrials.gov ID	NCT05436613
Funders	Milken Institute (financial support) Flow Neuroscience (provision of Flow tDCS device)

Contents

TRIAL SUMMARY	2
1 RATIONALE	5
2 OBJECTIVES AND OUTCOME MEASURES/ENDPOINTS	5
3 TRIAL DESIGN	7
4 TRIAL SETTING	7
5 PARTICIPANT ELIGIBILITY CRITERIA	7
6 TRIAL PROCEDURES	8
7 TRIAL TREATMENTS	10
8 RECORDING AND REPORTING OF ADVERSE EVENTS	11
9 STATISTICAL ANALYSIS PLAN	14
10 REFERENCES	17
11 SCHEDULE OF EVENTS	18

TRIAL SUMMARY

Trial Title:	Community-based transcranial direct current stimulation treatment for bipolar depression	
Short Title:	Transcranial direct current stimulation therapy for bipolar depression (b-DEP)	
Trial Design:	Pilot, open-label, single arm design	
Trial Participants:	Participants will have a diagnosis of Bipolar disorder, in a current depressive episode of moderate severity, receiving pharmacological or psychological treatment, ages minimum 18 years, community-dwelling.	
Total number of participants planned:	50	
Treatment duration:	6 weeks	
Additional follow up duration:	3 months	
Total trial duration per participant:	5 months	
Estimated total trial duration:	1 year	
Planned trial sites:	Multi-site	
	Objectives	Outcome Measures
Primary Objective:	To assess the efficacy of tDCS treatment	clinical response as measured by MADRS score improvement of $\geq 50\%$ following the course of tDCS treatment
Secondary Objective:	To assess acceptability and safety of the intervention.	Participant retention at the end of the treatment who have completed a minimum of 15 tDCS sessions. Participant acceptability questionnaire scales tDCS Adverse Events Questionnaire at each session

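### Section 6.1.2 makes major depressive disorder the MINI diagnosis required of bipolar participants, whereas 5.1.1 and the trial summary require bipolar disorder

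*Combined protocol and SAP*

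**What the plan says.** Three places in the combined protocol and SAP state the diagnosis a patient must have to enter.

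- **Trial summary, Trial Participants:** "Participants will have a diagnosis of Bipolar disorder, in a current depressive episode of moderate severity". The interview is not named here.
- **Section 5.1.1, Inclusion criteria:** "diagnosis of bipolar disorder based on DSM-5 criteria, with a current depressive episode of at least a moderate severity", followed by "diagnosis will be confirmed by the Mini-International Neuropsychiatric Interview".
- **Section 6.1.2, Screening:** "The screen assessment for participants with bipolar depression requires a DSM-5 diagnosis of major depressive disorder by a MINI interview assessment", together with "a minimum score of 18 on the MADRS".

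The schedule of events (section 11) marks the MINI once, at screening, and gives no target diagnosis.

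**The concern.** Diagnosis defines this trial's population, and 6.1.2 is the rule that screening staff apply. Read literally, it asks the MINI to establish a diagnosis other than the one 5.1.1 asks the same interview to confirm. A monitor checking MINI records against 6.1.2 would look for one diagnosis, and a monitor checking against 5.1.1 would look for another.

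The MINI is the only instrument the protocol names for confirming the diagnosis. Sections 6.1 and 6.1.1 allow recruitment through advertisements, social media and self-referral, so some candidates will arrive without a clinician's referral. The rule for that step should therefore name the right condition. What is at stake is the clarity of the entry rule; no numerical result is affected.

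**Working it through.** The point is one of wording, so there is no formula to apply and no figure of the plan to reproduce. The check sets the passages side by side.

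| Element | 5.1.1 Inclusion criteria | 6.1.2 Screening | Agree? |
|---|---|---|---|
| Patients | Bipolar depression sample | Participants with bipolar depression | Yes |
| Diagnostic system | DSM-5 | DSM-5 | Yes |
| Interview | MINI | MINI | Yes |
| Diagnosis to be established | Bipolar disorder, currently in a depressive episode | Major depressive disorder | **No** |
| MADRS minimum | 18 | 18 | Yes |

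1. **Where the conflict lies.** Every element matches except the named diagnosis. On severity, 5.1.1 reads "with a minimum score of 18, indicating at least a moderate severity of symptoms", and 6.1.2 uses the same score.

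2. **Which text is the outlier.** Of the three statements of the entry diagnosis, two (trial summary and 5.1.1) say bipolar disorder and one (6.1.2) says major depressive disorder. The latter term occurs only once in the whole document, in 6.1.2. Bipolar disorder or bipolar depression is named as the condition or patient group in the title and trial summary and in sections 1, 2, 2.6, 3, 5.1 (with 5.1.1), 6.1, 6.1.3 and 9.1. The direction of the correction therefore comes from the protocol itself.

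3. **Whether another passage reconciles them.** None does. The schedule is silent on the target diagnosis. Section 7.3 mentions major depression only as the indication for which the devices are CE marked, which is not an entry criterion.

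4. **Whether both diagnoses could be meant together.** The document does not say so. Section 5.1.2 excludes "any concurrent psychiatric disorder, including obsessive compulsive disorder" and writes no exception for major depressive disorder, which sits badly with a dual requirement. That exclusion can, however, be read as covering disorders other than the qualifying mood disorder. It does not settle the matter, and the finding does not rest on it.

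5. **Whether any number depends on it.** The sample size statement (d = 0.70, 90% power, 50 enrolled, 45 completing, 10% attrition) makes no use of the 6.1.2 wording. Nor does the response percentage defined in 9.3.2.

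**The case against.** The strongest reply is that the sentence largely corrects itself. It limits itself to participants with bipolar depression before it names the MINI diagnosis, and the rest of the protocol leaves no doubt about the intended population. The schedule also lists an inclusion and exclusion check at screening and once more afterwards, so the 5.1.1 diagnosis is checked whatever 6.1.2 says. The authors may have meant the current depressive episode, or they may have carried wording over from the unipolar pilot mentioned in section 1.1.

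Much of this stands, and it is why the point is minor. It does not make the text consistent. Both explanations are inferences that the document does not state. Section 6.1.2 names a disorder, not an episode, and 5.1.1 shows that the authors could write the intended rule when they meant it.

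Two smaller objections are fair. First, a two-to-one count of passages does not measure impact; the evidence is the direct comparison of 5.1.1 with 6.1.2. Second, in 5.1.1 the MINI confirms the diagnosis while the MADRS assesses severity, so a correction should keep those two roles apart.

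**Conclusion.** The inconsistency is real, and 6.1.2 is wrong as written: it attaches the wrong diagnosis to the MINI step for the trial's own patient group. The grade is minor. The practical impact is likely small, because the sentence itself names bipolar participants and section 5 governs eligibility. The document does not show that unipolar patients would be enrolled, and no effect on enrolment, the response rate or the safety estimates is claimed.

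The conclusion rests only on the current text of 5.1.1, 6.1.2 and the trial summary. It needs no assumption about how the wording arose.

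**What to change.** In 6.1.2, replace major depressive disorder with the diagnosis already set in 5.1.1. One way to write it is: *Screening of the bipolar depression sample requires that the MINI confirms the diagnosis specified in 5.1.1 (DSM-5 bipolar disorder, currently in a depressive episode) and that the MADRS score is 18 or more.*

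Referring to 5.1.1 keeps the rule in one place, and naming the two instruments separately leaves diagnosis with the MINI and severity with the MADRS. While editing, the authors could also align the severity wording: the trial summary says moderate, whereas 5.1.1 says moderate or worse.

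The cost is a one-sentence text correction, with no added procedure, assessment or analysis.

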6.1.3 Payment

Participants with bipolar depression will be reimbursed for their participation in the study: \$66. (£50. GBP) and for the EEG assessments: \$44. (£30. GBP).

Healthy control participants will be reimbursed £20 for their participation in the study.

Participants that travel to the research centre will be reimbursed for their travel expenses, up to a total of £20 per visit.

After the trial, participants will be able to keep the tDCS device if they would like to and will be provided with NICE tDCS for Depression most recent Interventional Procedures Guidance, published 26 August 2015 (<https://www.nice.org.uk/guidance/ipg530>).

